C2.4.1: Design Considerations and Justification: We discussed our careful considerations regarding our focus on the Cessation period and the use of this surrogate endpoint during a smoking cessation attempt in section A5 earlier. We also carefully considered an alternative design where we measured negative affective response during a single session of NRT administration to deprived smokers in the laboratory rather than at one week into a quit attempt. Although this alternative would be simpler, it may fail to capture a number of critical elements that are relevant to real-world quit attempts. In particular, the affective experience is likely quite different during a temporary deprivation period vs. a similar duration of deprivation in the context of an intended permanent cessation of use. Furthermore, the effects of deprivation likely vary over time during the cessation attempt as regulatory resources become drained and homeostatic adaptation processes are recruited (104,129–131). Our current design indexes negative affect both early in deprivation (during the pre-quit deprived session) and after one week of cessation. In addition, the 2 week quit period provides the opportunity for detailed real world measurement of stressor-affect, stressor-urge, and stressor-smoking relations via EMA (see below) that would not be available with the single NRT administration in the laboratory. We believe these benefits justify our current design.

Participants are instructed to continue NRT even if they fail to maintain complete abstinence during their quit attempt. There is evidence that participants benefit from reduced smoking on NRT even if full abstinence is not obtained or maintained (20). This procedure will allow all participants to be included in analyses of EMA cessation measures. Furthermore, analyses of the cued threat task that is administered at one week post-quit can retain all participants but include regressors/covariates to model the amount of smoking (and medication use) during the first week.

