C3.1: No-Shock/Predictable/Unpredictable (NPU) Threat Task. In this task, participants will view a series of colored square cues" displayed in the center of a computer screen with a black background. We presented cues in a blocked design with three conditions: no-shock (N), predictable shock (P), and unpredictable shock (U). Each shock condition is presented twice and separated by no-shock condition. Condition order is counterbalanced both within and between subjects (i.e., two condition orders: PNUNUNP, UNPNPNU), and participants complete the same order at both study visits. All blocks include six cues presented for 5 s separated by a variable intertrial interval (ITI; mean 17 s, range 14–20 s). A white fixation cross remains in the center of the monitor during the cues and ITI. We administer a 200-ms electric shock 200 ms prior to cue offset during every cue in the predictable shock condition, so that the appearance of the cue "predicts" that the shock will occur in several seconds. We administer electric shock at pseudorandom times during both cues and ITIs in the unpredictable shock conditions, so that the occurrence of the shock is unpredictable by the participant. Shocks occur 2 or 4.8 s postcue onset and 4, 8, or 12 s post cue offset in the unpredictable condition. Twelve electric shocks are administered in each predictable and unpredictable shock condition. No electric shock occurs during the no-shock condition. Each block lasts approximately 150 s, and the entire NPU task lasts approximately 20 min..

Startle probes occur at 4.5 s post cue onset on a random subset of eight cues and 13, 14, or 15 s postcue offset during four ITIs in both shock conditions (no-shock condition: twelve cues and six ITIs). Startle probes occur a minimum of 12.5 s after another startle-eliciting event (e.g., shock or startle probe). Serial position of startle probes across the three conditions for both cues and it is counterbalanced within subjects to account for habituation. We use two different orders of the serial position of startle probe, counterbalanced between subjects.

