C3.2: Psychophysiological Measurement. Startle potentiation is the primary dependent measure from the cued threat tasks. Acquisition and scoring of the eyeblink startle response will follow well-established procedures described in the Society for Psychophysiological Research guidelines paper (136). The startle response will be elicited by acoustic probes (50 ms, 105 dB white noise with near instantaneous rise time) and measured by recording electromyographic (EMG) activity in the orbicularis oculi muscle. Startle electromyographic activity will be sampled (2500 Hz) and filtered (500 Hz low-pass) online with Neuroscan Synamps II amplifiers. Offline processing includes high-pass filtering (28 Hz high-pass 4th order Butterworth filter), signal epoching (-50ms to 250ms relative to acoustic probe), rectification, and smoothing (30 Hz low-pass 4th order Butterworth filter). Peak eyeblink startle response is scored between 20-100 ms post-probe onset relative to mean 50 ms pre-probe baseline. Our laboratory has used these procedures in published research involving drug administration and deprivation for over a decade (33,34,58,64,86,137,138). Startle

potentiation scores are calculated as the increase in startle response during threat vs. no-threat conditions separately for certain and uncertain threat conditions.

We will also collect two secondary measures of affective response (corrugator electromyographic activity, and electroencephalography (EEG)) to measure facial display of affect and general arousal, respectively, in response to certain and uncertain threat cues. Participants will be prepared for recording by using AgAgCl sensors filled with a conductive gel and placed on various facial muscles (EMG includes orbicularis oculi – under left eye; corrugator –over left eyebrow) as well as on the scalp (EEG). Additionally two AgAgCl sensors will be placed on the forehead to act as ground and reference sensors. Acquisition and scoring of these measures will also follow well established procedures (139–141). Our laboratory has regularly collected these measures as part of a standard battery of peripheral psychophysiological measures of negative affective response (137,142–145).

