Additional covariates will be considered for each GLM to reduce error variance and increase power (e.g., resting startle response, task order, block order). All experiments include equal numbers of men and women to allow for preliminary examination of possible sex effects. Trait individual difference variables (e.g., individual differences in anxiety, depression, levels of tobacco dependence; see section C2.2) can be included in the GLMs to provide exploratory tests for potentially interesting moderators. Quantitatively measured withdrawal symptoms (WSWS) and smoking urge (QSU) can be included in supplemental analysis to clearly link deprivation status effects on startle potentiation to these proximal processes. Given that all participants complete both threat tasks, follow-up GLMs can include task as a within-subject factor to determine if effects are consistent across tasks that involve different manipulations of anxiety (i.e., low probability vs. temporally uncertain threat). This will provide important construct validation and potential conceptual replication of possible anxiety findings.

Analysis of Ecological Momentary Assessments of Stressors, Affect, Urge and Smoking (AIMS 2, and 4.3)

Analysis of EMA data will follow directly from procedures described by our Co-I, [name], in McCarthy, Piasecki, Fiore, & [name] (2006). Although the focal questions in McCarthy et al (2006) were different, the nature of that dataset was very similar in that it included multiple weeks of 4X daily EMA reports of stressors,

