affect, cigarette use, and withdrawal symptoms. The within-subjects, repeated measures design associated with EMA survey make it suitable for **growth-curve modeling**, a technique that estimates change over time via **multilevel modeling** (147,148). Although time is not a focal factor in our analysis, growth curve modeling is well-suited for these data and our questions because it can easily accommodate missing data and unequal intervals between assessments that result from pseudo-randomly selecting assessment times during each day. This multilevel model allows us to predict “occasion-level” (level 1) responding associated with affective response, urge, or smoking with other occasion-level variables (e.g., stressor occurrence), or “person-level” (level 2) variables (e.g., startle potentiation measures from cued threat task). Therefore, these models will provide clear and powerful tests to determine if laboratory startle potentiation “biomarkers” of stress neuroadaptations predict individual differences in overall levels of negative affect, urge, or smoking over the 3-weeks of EMA controlling for stressor exposure (AIM 2.1). Furthermore, these same models will provide tests if startle potentiation measures of stress neuroadaptation predicts individual differences in the size of the occasion-level stressor effects on negative affect, urge and smoking (i.e., stress-induced negative affect, urge, and smoking). In other words, do our laboratory stress neuroadaptation measures predict stressor-affect, stressor-urge, and stressor-smoking covariation or coupling over time (AIM 2.2). Treatment condition can be included as a moderating between-subject factor to test if the relationship between startle potentiation and overall levels and coupling of EMA measured affect, urge and smoking differ generally when withdrawal symptoms are treated via combo NRT (AIM 4.3). As with GLM analyses, these multilevel models can accommodate other exploratory person-level moderators of these effects (e.g., trait anxiety, depression, level of dependence, sex). As before, the models can also include task as a factor to determine if anxiety as measured in the laboratory task displays comparable relationships with occasion-level EMA data

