Analysis of Treatment Outcome (AIMS 3, 4.1, 4.2): Number of cigarettes smoked (17,18), point prevalence abstinence and continuous abstinence (as defined by the SRNT Workgroup on Biochemical Confirmation (149)) will be analyzed in Generalized Linear Models with time (1 week vs. 2 weeks) as a within subject factor. Startle potentiation measures from the cued threat task will be included as quantitative regressors to test if our laboratory stress neuroadaptation biomarkers predict treatment outcome measures (Aim 3). As above, treatment condition can be included as a moderating between subject factor to test if the relationships between startle potentiation and treatment outcome differ generally when withdrawal symptoms. Finally, mediation analyses can be conducted to determine if NRT alters startle potentiation measures at one-week post quit (AIM 4.1) and the startle potentiation measures mediate NRT effects on smoking outcome measures (AIM 4.2).

C4.3: Sample Size Justification. The primary analyses of startle potentiation will be accomplished within the General Linear Model (GLM). The analyses of smokers test for a two way interaction between Deprivation Status and Threat Uncertainty. Cohen (150) defines 0.15 for the squared multiple partial correlation as a medium effect size for GLM analyses. To be conservative, we powered our experiments to provide 90% power to detect a somewhat smaller (0.10) effect size. N=142 will provide 90% power to detect a squared multiple partial correlation of 0.10 for the interaction in a model that contains the two main effects and interaction based on formula provided by Cohen. We then increased this sample size to the round 150 within each Treatment Group to provide flexibility to counterbalance all relevant additional task factors. This yields N=300 across the two Treatment Groups. Given that the multilevel models that will be used to test questions about the EMA data are essentially GLMs fit at two separate levels of analysis (occasion and person levels), N=150 within each Treatment Group will provide comparable high power to test person-level predictors of both occasion-level intercepts (e.g., overall smoking, levels of negative affect) and stressor coefficients (e.g., stress-instigated smoking or negative affect).

DATA AND RECORD KEEPING

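### If startle habituation is curved, the assigned NPU block order adds avoidable noise to the separate certain and uncertain scores; the plan should commit to removing it (low priority, nearly free)

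*Combined protocol and SAP*

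**What the plan says.** Section C3.1 sets seven blocks in "two condition orders: PNUNUNP, UNPNPNU" and adds that "participants complete the same order at both study visits". On habituation it says: "Serial position of startle probes across the three conditions for both cues and it is counterbalanced within subjects to account for habituation". There are also two probe-position orders, balanced between subjects.

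Section C3.2 defines the scores: "potentiation scores are calculated as the increase in startle response during threat vs. no-threat conditions separately for certain and uncertain threat conditions". No order adjustment is part of the definition.

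Under Statistical Considerations:
- **Aim 1:** "Additional covariates will be considered for each GLM to reduce error variance and increase power (e.g., resting startle response, task order, block order". No interaction between block order and Threat Uncertainty is named.
- **EMA models (Aims 2 and 4.3):** "these multilevel models can accommodate other exploratory person-level moderators of these effects". The examples are traits, dependence and sex, and task is also mentioned. Block order is not.
- **Treatment outcome (Aims 3, 4.1, 4.2):** "Startle potentiation measures from the cued threat task will be included as quantitative regressors", again without an order term.

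For the post-quit threat task, section C2.4.1 says the analysis can "include regressors/covariates to model the amount of smoking (and medication use"; order is not listed.

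**The concern.** In the first order, predictable-shock (P) blocks are 1 and 7 and unpredictable-shock (U) blocks are 3 and 5. In the second order they swap. The no-shock (N) blocks are 2, 4 and 6 in both. If startle drops quickly at the start and then levels off, blocks 1 and 7 together give a larger response than blocks 3 and 5. Whichever threat condition has the outer positions is inflated relative to the other. N sits in the same places in both orders, so subtracting it leaves the difference intact. Balancing probe position does not change which threat condition occupies block 1.

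Using two orders balances group means, but each individual's score still carries the shift of the assigned order. Aims 2, 3 and 4.3 use those individual scores as predictors, so the result is attenuated slopes and lost precision from a factor that the trial itself assigns and can adjust for.

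**Working it through.** **The plan's own figure.** Section C4.3 gives N=142 for 90% power at an effect of 0.10. Alpha is not stated; 0.05 is assumed. With 0.10 taken as f² and 3 numerator df, L=14.17 and L/f² = 14.17/0.10 = 141.7, so 142. The exact noncentral F gives N=146, and power 0.892 at N=142. Read literally, as a squared partial correlation of 0.10 on 1 df (f² = 0.10/0.90 = 0.111), the answer is N=97. Both readings are carried below.

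**Linear drift.** Mean serial position is (1+7)/2 = 4 for the outer pair, (3+5)/2 = 4 for the inner pair and (2+4+6)/3 = 4 for N. The order shift is exactly zero.

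**Curved habituation (assumed).** Let f(k) = 1 + a·exp(-l(k-1)) at block k, in units of the habituated startle size. With a=0.6 and l=0.4:
- Outer: (1.600 + 1.054)/2 = 1.327.
- Inner: (1.270 + 1.121)/2 = 1.195.
- Difference Δ = 0.132.

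With a=0.6 and l=0.7, Δ = 0.212.

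U-P is -Δ in one order and +Δ in the other. U alone moves by ±Δ/2 about its mean, and P by the same amount the other way. The mean of P and U does not move.

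**Share of variance.** With half the orders each way, w = s²/(1+s²), where s is the shift divided by the within-order SD. That SD is assumed to be 0.4 for either score.

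| Δ | U-P: s = Δ/0.4 | w | U alone: s = (Δ/2)/0.4 | w |
|---|---|---|---|---|
| 0.05 | 0.125 | 2% | 0.0625 | 0.4% |
| 0.132 | 0.330 | 10% | 0.165 | 2.6% |
| 0.212 | 0.530 | 22% | 0.265 | 6.6% |

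These are not bounds. A flatter curve (a=1.0, l=0.1) gives Δ=0.03 and w=0.6% for U-P. A steeper one (a=1.0, l=0.7) gives Δ=0.354, with w=44% for U-P and 16% for U alone. When the score is a predictor, its slope shrinks by the factor 1-w, whatever the sample size.

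**Power.** Let d be the gap between orders in within-order SDs. Then w = (d²/4)/(1+d²/4), and the effect falls from 0.10 to 0.10(1-w).

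| d | w | N=150, f²=0.10, 3 df |
|---|---|---|
| 0 | 0 | 0.909 |
| 0.2 | 1.0% | 0.906 |
| 0.4 | 3.8% | 0.897 |
| 0.6 | 8.3% | 0.881 |
| 0.8 | 13.8% | 0.859 |
| 1.0 | 20% | 0.829 |

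Over the same range (d from 0 to 1.0):
- On the literal 1-df reading, N=150 goes from 0.982 to 0.948, and N=300 stays above 0.999.
- For a smaller assumed effect (partial R² 0.03, 1 df) at N=300, power goes from 0.859 to 0.773.

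**Where the noise stays and where it cancels.** Order is the same at both visits, so a stable shift cancels in the pre-to-post change that is the Aim 4.2 mediator and in any within-person contrast. For Aim 1 the documents conflict. The Aim 1 analysis text treats deprivation as a within-subject factor over two pre-quit sessions. Sections C2.3 and C3 give each person one early session, deprived or non-deprived. On that between-person reading the noise stays. It also stays in the Aim 2, 3 and 4.3 predictors, and in a post-quit Aim 4.1 comparison of the uncertain score.

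**Why a main effect is not enough.** The mean of P and U does not depend on order, so an order main effect takes nothing out of the uncertainty contrast; order by Threat Uncertainty does. Likewise, write a person's score as S = T + h·o, with o = ±1 for order. The product of S with stressor then contains h·o × stressor, which an order main effect leaves in place. The same holds for S by treatment in Aim 4.3.

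**The case against.** The strongest reply is that the design already deals with habituation. Both orders remove linear drift, probe position is balanced within subjects, and no habituation curve or order effect is reported. That stands: the shift is conditional on curvature, and its size is unknown.

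A second reply is that block order is already a candidate covariate, and that in a model of the within-subject contrast a between-subject order term is the interaction. This is a fair reading of common practice, and the section describes itself as a sketch. But the text neither commits to the term nor states its form, and nothing equivalent appears where startle is a predictor.

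Third, power at N=300 barely moves at the design effect. That is correct. Slope attenuation, however, does not shrink with N.

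A reader might infer that order noise weakens every test, or that the Aim 2 to 4 slopes lose 10-22%. The documents support neither. The shift cancels in several analyses, as set out above. The 10-22% belongs to the difference score, whereas section C3.2 scores certain and uncertain threat separately and nothing says that the predictor is their difference.

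**Conclusion.** The point holds as a conditional, low-priority improvement. If habituation is curved, block order adds noise of opposite sign to the two threat scores. On the assumed curves and an SD of 0.4, this is about 2-22% of the variance of the uncertain-minus-certain score and about 3-7% of the uncertain score alone for the mid-range curves. It affects Aim 1 if the deprivation contrast is between persons, the Aim 2, 3 and 4.3 predictors, and a post-quit Aim 4.1 comparison of the uncertain score.

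The effect is lost precision and attenuation. A reader might go further and infer bias or false positives. That does not follow, provided order is independent of deprivation and treatment assignment. The order is counterbalanced, though the documents do not say whether it is balanced within those groups.

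The result rests on the curve shape, the SD, alpha 0.05 for the power figures, and reading Threat Uncertainty as U versus P in the NPU task. The analysis section still describes that factor through two other tasks.

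**What to change.** - **Aim 1 startle model:** replace the optional wording with a commitment to block order and block order by Threat Uncertainty, and the same pair for probe order.
- **Aims 2, 3 and 4.3:** wherever startle is a person-level predictor, use scores centred within block order and probe order. Alternatively, enter the order terms together with their interaction with stressor or treatment wherever startle has that interaction.
- **Aim 4.1:** include the order terms as covariates when post-quit startle is the outcome.
- **Aim 4.2:** no change is needed for a stable order effect in the change score.

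Both order variables are assigned by the trial, so no new data are needed. The cost is a few degrees of freedom out of 300. If the order effect proves small, almost nothing is lost.

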Our focus on smoking cessation outcome after 2 weeks follows important developments in the biomedical sciences. For example, David Kessler, former FDA Commissioner, has observed that the considerable advances in AIDS research can be attributed, in part, to the development of "**surrogate endpoints**" such as HIV viral load that index treatment effects in randomized clinical trials (RCT) far earlier than the obvious clinical endpoint of survival duration (13,14). Kessler advocated the development of such surrogates for other diseases: measures that would index effects that are linked with ultimate outcomes, but that can be obtained relatively quickly and cheaply relative to such outcomes. To this end, our two-week endpoint in this application was chosen to completely capture the "Cessation phase" of a quit attempt (14). The Cessation phase is a period when withdrawal symptoms (negative affect, urge to smoke) tend to be at their peak levels for many smokers (47,101,102) and play an important role in precipitating lapses back to smoking (103,104). Stressors also increase the likelihood that a person will lapse during this period (51,105). Initial smoking lapses are more likely in these first 2 weeks of the quit attempt than at other times, and such lapses are highly likely to transition into full relapse (106). As such, we believe that detailed momentary assessment of the first two weeks post-quit is most critical to evaluate the relationship between stressors, affect, urge, and cigarette use, and our psychophysiological indices of negative affective response to uncertain stressors from the laboratory. Although innovative, this focus on a two-week surrogate endpoint as a resource efficient proxy for long term smoking cessation outcome is also not without precedent in the smoking literature (15–19). For example, Perkins, Lerman and others have validated a new procedure to develop and screen medications for tobacco dependence that involves measuring number of days of abstinence during two weeks of medication use vs. placebo. They have validated the sensitivity of this surrogate two week endpoint in detecting efficacy for both NRT and varenicline (17,18). We propose similar quantification of smoking (number of days of abstinence), as well as stressor-affect, stressor-urge, and stressor-relapse relationships across this two week Cessation Phase as a surrogate endpoint to validate the clinical importance of our laboratory measures of negative affective response (anxiety) to uncertain stressors in the laboratory.

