1.1: Nicotine deprived smokers will display selectively increased negative affect measured via startle potentiation during uncertain (vs. certain) threat relative to non-deprived smokers.

AIM 2: Examine the impact of stress neuroadaptation on negative affect, smoking urge, and smoking in response to stressors. Laboratory startle potentiation measures of stress neuroadaptation will predict ecological momentary assessment measures of:

2.1 ...overall levels of negative affect and urge
2.2 ...within-smoker covariation (i.e., coupling) of episodic stressors with negative affect, urge, and smoking (i.e., stressor-induced negative affect, urge and smoking).

AIM 3: Examine the impact of this stress neuroadaptation on smoking during the first two weeks of smoking cessation.

3.1: Laboratory startle potentiation measures of stress neuroadaptation will predict overall smoking during the first two weeks post-quit as well as measures of point prevalence abstinence and continuous abstinence measured at 2 weeks post-quit.

AIM 4: Determine if treatment of withdrawal via NRT reduces the influence of stress neuroadaptation.

4.1: Combo NRT with counseling (vs. placebo NRT with counseling) will reduce startle potentiation measures obtained at one week post-quit.

4.2: The effect of combo NRT (vs. placebo NRT with counseling) on smoking and related outcome measures will be mediated by change in startle potentiation measures from pre-quit to post-quit.

4.3: Treatment of withdrawal symptoms via combo NRT will attenuate the predictive strength of pre-quit startle potentiation measures with respect to overall levels of negative affect, urge, and smoking and stressor-induced negative affect, urge, and smoking.

RESEARCH DESIGN AND METHODS

C1: BRIEF OVERVIEW

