These EMA data are collected to evaluate the relationships between individual differences in psychophysiological affective response in our cued threat task (overall and deprived vs. non-deprived negative affect generally and fear/anxiety selectively) and real time, *in vivo*, affective response, smoking urge, and cigarette use. We will test if our laboratory-assessed psychophysiological individual differences predict individual variability in affective response, urge, and cigarette use recorded via EMA. We will also examine stress-affect, stress urge, and stress-smoking coupling (i.e., temporal covariation over 2 weeks post-quit between stressor experience, strength of affective response, and cigarette urge and use). We will also examine if any of these relationships differ across (i.e., are moderated by) Treatment Groups (Combo NRT with counseling vs. placebo NRT with counseling).

C2.5.1: Design Considerations and Justification. The use of EMA methods with 4X daily reports allows for increased precision with respect to temporal ordering of stressors, affect, smoking urge, and cigarette use. The survey was kept brief to decrease assessment burden. Similar (and longer) length surveys have been completed with high compliance (> 80% response rates) in Drs. [name] and [name]'s research with community smokers. We acknowledge that these reports are subjective based on the participants' individual appraisal of stressor severity and their own affective response to these stressors. However, these individual differences are at the core of our predictions regarding increased negative affective response across stressors among smokers, particularly when nicotine deprived. We predict that our laboratory measures will identify the smokers who will show consistently strong negative affect generally and in response to aversive stressors, and that these smokers will have poorer smoking cessation outcomes.

C2.6: Post-Quit Laboratory Visit

We will measure treatment adherence, additional treatment/medication usage, stressors, affective status, withdrawal, urge, and cigarette use for smokers at a follow-up laboratory visit at 2 weeks post-quit. This visit will also allow for biological confirmation of smoking status via CO measurement (CO < 6ppm).

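### Aim 4.3 has no post-quit window or quit-phase term for negative-affect and urge levels; a pooled three-week model would dilute the treatment moderation to about two thirds

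*Combined protocol and SAP*

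**What the plan says.** **Aim.** Specific Aims, Aim 4.3, predicts: "Treatment of withdrawal symptoms via combo NRT will attenuate the predictive strength of pre-quit startle potentiation measures with respect to overall levels". The outcomes it lists are affect, urge and smoking, each both overall and in response to stressors. It states no time window.

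**Statistical section (Analysis of Ecological Momentary Assessments, Aims 2 and 4.3).** The window appears once, in the Aim 2.1 sentence: startle measures are to "predict individual differences in overall levels of negative affect, urge, or smoking over the 3-weeks of EMA controlling for stressor exposure (AIM 2.1"). The next sentence moves to coupling (Aim 2.2): "these same models will provide tests if startle potentiation measures of stress neuroadaptation predicts individual differences". Here the differences meant are those in how strongly stressors act on each smoker. Aim 4.3 follows: "Treatment condition can be included as a moderating between-subject factor to test if the relationship between startle potentiation and overall levels and coupling" differs when withdrawal is treated. On time, the section says only: "Although time is not a focal factor in our analysis". It names no pre/post-quit term.

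**Protocol body.** Section C2.5 splits the EMA into one pre-quit week and two post-quit weeks at four reports a day. It defines coupling as "temporal covariation over 2 weeks post-quit between stressor experience, strength of affective response, and cigarette urge and use", and then adds: "We will also examine if any of these relationships differ across (i.e., are moderated by) Treatment Groups". Section A5 likewise refers to "stressor-affect, stressor-urge, and stressor-relapse relationships across this two week Cessation Phase as a surrogate endpoint", and C2.4.1 ties the EMA measurement of stressor relations to the two-week quit period. Section C2.4 describes two weeks of medication.

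**Smoking.** Aim 3.1 and the Analysis of Treatment Outcome section place smoking after the quit date (1 week vs. 2 weeks), with treatment available as a moderator. For smoking, only the EMA version of the outcome is open.

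**The concern.** Aim 4.3 is about what happens while withdrawal is being treated. A third of the EMA reports come from the baseline week, when participants have not yet quit. If a levels model pools all three weeks and contains no phase term, the treatment-by-startle coefficient is an average over treated and largely untreated time. It is then smaller than the effect the aim describes. A real attenuation could be missed, or reported as weaker than it is.

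For negative-affect and urge levels, nothing elsewhere in the plan corrects this, because the three weeks attached to Aim 2.1 are the only window given. For coupling, the protocol body does supply a window. The issue there is that the statistical section should repeat it.

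**Working it through.** **The plan's own figure.** The only sample-size calculation (C4.3) is N=142 for 90% power at an effect of 0.10 in the Deprivation Status x Threat Uncertainty model. It is then extended to the EMA models. With alpha 0.05 two-sided (assumed; none is stated), 0.10 read as f² and 3 numerator df, I get N=146 and power 0.892 at N=142, so it approximately reproduces. It was not derived for a treatment-by-startle moderation, so 0.10 is only borrowed below.

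**Share of reports (C2.5).** 21 days x 4 = 84 prompts: 7 x 4 = 28 pre-quit (28/84 = 0.33) and 14 x 4 = 56 post-quit.

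**Dilution.** Let the post-quit moderation be 1 and the pre-quit moderation be p, with days weighted equally. The pooled estimate is (14 + 7p)/21.
- p = 0: 14/21 = 0.67
- p = 0.25: 15.75/21 = 0.75
- p = 0.50: 17.5/21 = 0.83

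**Standardised loss for levels (p = 0).** Let the post-quit person-mean SD be 1, the pre-quit SD be k, and their correlation be r. The pooled mean is one third pre-quit plus two thirds post-quit, so its SD is sqrt(k² + 4 + 4rk)/3. The standardised effect relative to a post-quit analysis is (2/3) divided by that SD, or 2/sqrt(k² + 4 + 4rk). The documents give neither k nor r, so I assume k from 0.5 to 2 and r from 0.3 to 0.7:
- k = 0.5, r = 0.3: 2/sqrt(4.85) = 0.908
- k = 1, r = 0.5: 2/sqrt(7) = 0.756
- k = 2, r = 0.7: 2/sqrt(13.6) = 0.542

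**Illustrative power for levels.** Noncentral F with df 1 and 296, N=300, alpha 0.05, lambda = 300 x R²/(1 − R²) x ratio². Only the 0.10 appears in the plan; 0.05 and 0.02 are assumed.

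| Post-quit partial R² | lambda at ratio 1 | Post-quit power | Pooled, ratio 0.542 | Pooled, ratio 0.756 | Pooled, ratio 0.908 |
|---|---|---|---|---|---|
| 0.10 | 33.33 | >99.9% | 88% | 99% | 99.9% |
| 0.05 | 15.79 | 98% | 57% | 85% | 95% |
| 0.02 | 6.12 | 69% | 27% | 46% | 61% |

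**Baseline covariate, levels only.** At r = 0.5 and p = 0, the pre-quit mean removes r² = 0.25 of the residual variance, so lambda is divided by 0.75. Power becomes 99.6% at R² = 0.05 and 81% at 0.02.

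**Cost of fewer reports.** With 56 instead of 84 reports, the standard error of one smoker's stressor slope rises by up to sqrt(84/56) = 1.22.

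**The case against.** **Coupling.** A reader might infer that the plan contradicts itself, with three weeks in the statistical section and two in C2.5. The documents do not go that far. The three weeks are tied to Aim 2.1 levels, and the coupling sentence gives no number of weeks. C2.5, A5 and C2.4.1 all place coupling after the quit date. Reading the general phrase with the specific definition removes the conflict, and with it any claim that two coupling windows are on offer. What remains is that the reference to the same models is ambiguous.

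**The phase term.** The statistical section defers to a published diary study for its EMA procedure, and describes the method as growth-curve modelling. It also introduces itself as giving exemplars only. A phase term may be in that cited procedure, which cannot be seen here, and calling time non-focal does not exclude it from the model. This lowers the certainty. It does not put a phase term, or a post-quit window for affect and urge levels, into the plan's own text.

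**Medication start.** Section C2.3 dispenses after the first laboratory session, which is before quitting in one group and the day after the start of the quit attempt in the other. A reader might infer that use could begin days before quitting, so that a post-quit window would miss treated time. Dispensing is not first use, however, and C2.6 and C3.3 place the 2-week visit during medication use. Two weeks of use begun several days early would not reach that visit. The passages need reconciling, but they do not support the early-start reading.

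**Size.** The test is secondary and worded as optional. At the one effect size the plan states, pooled power stays at 88% or more, so the figures do not show an underpowered trial. This stands, and it limits the severity.

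**Conclusion.** The point holds for Aim 4.3 levels of negative affect and urge, and for the EMA version of smoking. The plan's text gives only a three-week window, tagged to Aim 2.1, and no quit-phase term. Followed as written, the pooled moderation is about 0.67 of its post-quit size. That assumes no moderation before quitting, equal weighting of days, and two weeks of medication falling in the post-quit period; with some pre-quit moderation the loss is smaller (0.75 to 0.83 in the cases shown). The power figures also rest on assumed k, r, alpha and, apart from the borrowed 0.10, assumed effect sizes. They are illustrations, not estimates for this trial.

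For coupling, the finding is only that the statistical section should be aligned with C2.5. Severity is minor to moderate, confidence is medium, and the change is a cheap improvement.

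**What to change.** In the EMA analysis section, state the window for each aim.

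- **Aim 4.3 levels (negative affect, urge, EMA smoking).** Analyse the post-quit reports with the smoker's pre-quit-week mean of the same item as a person-level covariate. Also report the model without it, because the covariate changes the startle main slope to prediction given baseline. In a simulation with k = 1 and r = 0.5, that slope moved from 0.30 to 0.15 while the startle-by-treatment estimate was unchanged. Alternatively, keep all three weeks, add Phase x Treatment x Startle, and read Aim 4.3 from the post-quit effect.
- **Coupling (Aims 2.2 and 4.3).** State that it uses the two post-quit weeks, as in C2.5. Claim no covariate gain here.
- **Aim 2.1.** May stay at three weeks.
- **Cited procedure.** If it already contains a phase term, write that term into the plan.
- **Medication timing.** Reconcile the dispensing times in C2.3 with C2.6 and C3.3, so that it is clear which EMA reports precede medication.

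The cost is analysis wording; no new data are needed. The price of a post-quit window is fewer reports per person (56 rather than 84), with the loss of individual slope precision shown above.
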